5.6 APPROPRIATENESS OF MEASUREMENTS

All measurements performed during this trial are standard measurements in UC treatment trials and will be performed in order to monitor safety aspects or assess treatment response in an appropriate way.

Therefore, the appropriateness of all measurements applied in this trial is given.

6. INVESTIGATIONAL PLAN

6.1 VISIT SCHEDULE

All patients are to adhere to the visit schedule as specified in the [Flow Charts](#). Each visit date (with its window) up to EOT is to be counted from Day 1. If any of these visits has to be rescheduled, the date of subsequent visit should be calculated from Day 1. EOT refers to the last dose administration of BI 655130 (SPESOLIMAB) at week 336. Additional visits for the purpose of re-testing of laboratory parameters or AE monitoring may be included as deemed necessary by the investigator.

6.2 DETAILS OF TRIAL PROCEDURES AT SELECTED VISITS

Study procedures to be performed at each visit are listed in the relevant Flow Chart and the respective protocol sections. Refer to [Section 5](#) and [Section 10](#) (Appendices) for explanations of procedures. Additional details on procedures at selected visits are provided below.

Patient Reported outcomes (PROs) should be completed by the patient on his/her own in the pre-specified order in a quiet area/room before any other visit assessments or treatments and, as much as possible, before any interaction with the investigator or other members of the study team.

The order of completion for PROs is as follows, as applicable for each PRO at relevant visits according to the [Flow Chart](#):

1. IBDQ
2. EQ-5D-5L

6.2.1 Screening and run-in period(s)

Screening Period

After patients have been informed about the trial, written informed consent in accordance with GCP and the local legislation must be obtained prior to performing any study related procedures. Once they have consented, the patient is considered to be enrolled in the trial. The patient should be recorded on the subject enrolment log. Patient will be assigned a patient number and enrolment must be recorded in the eCRF pages.

Screening Visit (Visit 1):

The Screening visit (Visit 1) should occur 7 days before Visit M1 and be complete no less than 3 days prior to Visit M1.

At this visit, information will be collected for evaluation of trial eligibility as indicated in the [Flow chart 1](#) or [Flow chart 2](#).

Visit 1 should be performed in one visit, in combination with EOT visit of the previous induction trials 1368-0005 Part 1; 1368-0004. Procedures performed at EOT visit of previous trial should not be repeated at V1 of 1368-0017.

For more details regarding procedures at V1 please refer to [Flow chart 1](#) or [Flow chart 2](#).

Baseline Conditions

Chronic diseases, current observable conditions, any new clinically relevant findings discovered from the physical examination, ECG, safety labs, and any condition requiring therapy (excluding UC) will be reported on the baseline condition eCRF page.

Patients who have a laboratory test value outside the range specified by the inclusion criteria may have the test repeated to determine eligibility. The result must be available prior to Visit M1 (Day 1).

Demography

Informed consent date, gender, age, race and ethnic origin will be collected in the eCRF page. Also, the patient's smoking history will be assessed. Information concerning race/ethnicity will be collected, as it has been suggested that there may be race/ethnicity variations in the incidence, phenotypic manifestations and outcome of UC. Note: In some countries, race may not be collected.

Medical and Surgical History

Information on clinically significant previous and concomitant diseases, other than UC, should be registered in Baseline conditions as follow up from the previous induction studies.

Blood sampling

Blood samples will be drawn for safety lab, PK, ADA and biomarkers. TSH and Glycosylated Hbc (HbA1c) does not need to be assessed at screening visit. These need to be assessed first at W36 of maintenance treatment period and then every 48 weeks. For women of childbearing potential, a serum pregnancy test will be performed.

Stool sampling

A stool sample will be collected for faecal biomarkers (calprotectin, lactoferrin).

Patient diary

Patients will use an eDiary provided at screening visit for reporting of stool frequency and rectal bleeding (blood in stool). Patients have to be asked to enter these data into the eDiary 14 consecutive days prior to each visit which includes assessment of Mayo score, and as well when a patient perceives worsening of UC symptoms at any time between visits as a precursor to disease flare assessment (see [section 3.1](#)).

The diary will be returned at EOS visit.

Visit 1.a

Visit 1a should take place approx. 3-7 days after Visit 1 when sigmoidoscopy assessment will be provided by central reader to finalize eligibility assessment. This visit can be done per telephone. Patients should be asked for any changes in concomitant therapy or potential AEs from V1.

6.2.2 Treatment period

The treatment period is lasting from Visit M1/R1 until End of Treatment (EOT) Visit.

Study related procedures during treatment period will be performed as specified in the [Flow chart 1](#), [Flow chart 2](#) or [Flow chart 3](#), in case patients develop a disease flare.

Patients can be discontinued from trial medication at any time if in the opinion of the Investigator, continuation with trial medication is not in the patient's best interest.

Pregnancy testing

Urine pregnancy testing for all women of child-bearing potential will be conducted on-site at visits with study drug administration (4 weeks during i.v. re-induction phase) and must be negative to continue treatment. More frequent testing should be done if required by the local regulation and / or authority or per investigator judgment.

The pregnancy testing should be done **prior to** study drug administration. A positive urine test must be confirmed with a serum pregnancy test.

Blood sampling

Blood sampling (e.g., for safety lab, BMs) should be done **prior to** study drug administration and **prior to** sigmoidoscopy, if applicable. It is not requested that patient is fasted prior to collection of the safety laboratory testing as indicated in Flowcharts, but patient has to be asked and information will be collected on lab requisition form if patient was fasting or not 8h prior to blood sampling

Sigmoidoscopies

Sigmoidoscopies will be done after blood sampling and **prior to** study drug administration. Sigmoidoscopies will be performed every 48 weeks during maintenance treatment period and at end of re-induction period as indicated in the Flowcharts. Additionally sigmoidoscopies have to be done in case of disease flare as indicated in Flowchart 3. During sigmoidoscopies, biopsies will be taken for endpoint evaluation at time points as indicated in the [Flow Chart](#). Please refer to Section 5 of the ISF for further information on the collection and the processing of biopsies.

Colonoscopy instead of sigmoidoscopy can be performed if required as colon cancer screening per local guidelines.

PK and ADA sampling

Blood sampling for PK assessments should be done within one hour **prior to** study drug administration.

Clinical monitoring after study drug administration:

The patient will be monitored for infusion reactions at the site for approximately 1 hour following study drug administration. Local tolerability at the administration site of the subcutaneous injection will be assessed by the investigator at the specified visits as noted in the [Flow Chart](#).

At all dosing visits vital signs will be assessed pre- and post-dose, please see [section 5.2.2](#) for further details.

Unscheduled visits

The patient may be asked for additional unscheduled visits due to safety reason at the discretion of the investigator or the sponsor, unless the patient has withdrawn his/her consent. The patient may also contact the site due to safety reason for an unscheduled visit. The unscheduled visit may include additional collection of blood samples for safety reasons. The unscheduled visit may also include additional assessments deemed necessary by the investigator such as laboratory samples, ECGs, or other procedures which were missed at a previous visit. All unscheduled visits should be described (including the reason for the visit) and documented in the medical/source record, and in the eCRF.

Concomitant medication review

Data concerning concomitant medications and procedures will be collected throughout the trial, as specified in the [Flow Charts](#). These data will be obtained at scheduled or unscheduled trial visits based on information provided spontaneously by the patient or as a result of questioning the patient.

6.2.3 Follow up period and trial completion

For all patients, termination of trial medication and trial completion must be recorded on the corresponding eCRF.

For patients completing the safety FU period, the EOS visit is scheduled at 16 weeks after the last dose of study drug. For more details please follow [Flow Charts](#).

6.2.3.1 Early treatment discontinuation

Patient who discontinue treatment prior to the planned EOT visit have to be invited for an early EOT visit as soon as possible. These patients should be registered as withdrawn from treatment in IRT and return to the site for the End of Study (EOS) visit 16 weeks after last study drug intake.

6.2.3.2 Trial completion

Patients who finish the treatment period will return to the site for the End of Study (EOS) visit 16 weeks after the EOT visit. Completion is defined as a patient having reached the EOS visit.

6.2.3.3 Further treatment after the end of the trial

At the end of the trial, patients will be treated for their UC at the discretion of the investigator, according to local UC guidelines (e.g. ECCO guideline [R17-0243](#)).

7. STATISTICAL METHODS AND DETERMINATION OF SAMPLE SIZE

7.1 STATISTICAL DESIGN - MODEL

This trial is designed as a single arm, open-label trial in patients with ulcerative colitis who have completed the planned treatment period in previous trials 1368-0004 or 1368-0005/Part 1. The following treatments are planned:

- For patients who do not have a clinical response at week 12 of parent trial:
 - Multiple active doses of intravenous BI 655130 (SPESOLIMAB) 1200 mg q4w to be administered for 12 weeks (re-induction); responders at week 12 will subsequently receive subcutaneous BI 655130 (SPESOLIMAB) 300 mg q4w as maintenance treatment for up to 7 years;
- For patients who do have a clinical response at week 12 of parent trial:
 - Subcutaneous BI 655130 (SPESOLIMAB) 300 mg q4w as maintenance treatment for up to 7 years.

Patients who experience a disease flare (as defined in [section 2.1](#)) will be administered disease flare rescue medication as a single dose of BI 655130 (SPESOLIMAB) 1200 mg followed by an intensified maintenance dosing schedule with 600 mg q6w.

For both efficacy and safety data, the following reporting periods will be defined:

- Maintenance Period
 - Includes data from the maintenance part of this extension trial.
- Re-Induction Period
 - Includes data from the re-induction part of this extension trial, where applicable.

There is no confirmatory statistical testing planned during the analysis of this extension trial; only descriptive analyses are intended.

7.2 NULL AND ALTERNATIVE HYPOTHESES

Given the single arm and open-label nature of this trial, all statistical assessments will be performed in a descriptive manner only. No hypothesis testing is intended to be performed.

7.3 PLANNED ANALYSES

There will be 2 main patient populations in this trial for analyses: the treated set for maintenance treatment (TS-MT) and the treated set for re-induction treatment (TS-RT).

Treated Set for Maintenance Treatment (TS-MT)

This patient set includes all patients who received at least one dose of maintenance treatment in the extension trial. It will be the main analysis set for presentation of safety and efficacy during the maintenance part of the extension trial.

Treated Set for Re-induction Treatment (TS-RT)

This patient set includes all patients who received at least one dose of re-induction treatment in the extension trial. It will be the main analysis set for presentation of safety and efficacy during the re-induction part of the extension trial.

Further analysis sets will be defined in the TSAP if necessary.

Important violations of the protocol will include violations of the key inclusion and exclusion criteria, concomitant use of restricted medications, and any other violations of the protocol deemed important by the study team. All decisions concerning important protocol violations will be made prior to final database lock for this extension trial.

Standard statistical parameters (number of non-missing values, mean, standard deviation (SD), median, quartiles, minimum and maximum) or frequency tables (including patient frequencies and percentages) will be calculated where appropriate.

A Clinical Trial Report will be prepared once the final database lock for this extension trial has been performed.

7.3.1 Primary endpoint analyses

Refer to [section 7.3.4](#) for the description of safety analyses including that for the primary endpoint. The primary endpoint will be summarized for the maintenance period (described in [section 7.1](#)).

7.3.2 Secondary endpoint analyses

The evaluation of clinical outcomes based on the Mayo Clinical Score, i.e. clinical remission, is based upon the endoscopy results obtained from central reading. Only if the centrally read endoscopy result is missing at a time-point will the locally read result be used instead.

For the stool frequency and rectal bleeding items reported in the patient diary, an average of the last 3 non-missing daily assessments collected within the last 7 days prior to the applicable visit will be used for the determination of clinical outcome. If the patient

undergoes bowel preparation for endoscopy on any of the days before a visit, the stool frequency and rectal bleeding subscores on that day(s) should be considered to be missing. In addition, the stool frequency and rectal bleeding subscore will be considered to be missing both on the day of and the day after the endoscopy.

Secondary endpoint will be assessed descriptively. Further details will be provided in the TSAP.

7.3.4 Safety analyses

Adverse events will be coded using the Medical Dictionary for Drug Regulatory Activities (MedDRA). Standard BI summary tables and listings will be produced. All adverse events with an onset between start of treatment and end of the residual effect period (REP), a period of 16 days after the last dose of trial medication, will be assigned to the on-treatment period for evaluation. Adverse events occurring in the maintenance and re-induction periods will be separately described.

All treated patients will be included in the safety analysis. In general, safety analyses will be descriptive in nature and will be based on BI standards. No hypothesis testing is planned.

Statistical analysis and reporting of adverse events will concentrate on treatment-emergent adverse events, i.e. all adverse events occurring between start of treatment and end of the residual effect period. For patients who switch directly to maintenance treatment at week 12 of the re-induction period, adverse events occurring on and after the first day of maintenance treatment will be included in summaries of the maintenance period only. Adverse events that start before first drug intake and deteriorate under treatment will also be considered as 'treatment-emergent'. For all subjects who received disease flare treatment with BI 655130 (SPESOLIMAB), safety assessments including adverse events, laboratories, vital signs etc. which occurred subsequent to such intake will be excluded from presentations according to the planned treatment; these data will, however, be included in summaries where all data after any use of BI 655130 (SPESOLIMAB) are displayed.

Frequency, severity, and causal relationship of adverse events will be tabulated by system organ class and preferred term after coding according to the current version of the Medical Dictionary for Drug Regulatory Activities (MedDRA) at the database lock.

Laboratory data will be analysed both quantitatively as well as qualitatively. The latter will be done via comparison of laboratory data to their reference ranges. Values outside the reference range as well as values defined as clinically relevant will be summarised.

Laboratory data will be analysed descriptively with regard to distribution parameters as well as with regard to frequency and percentage of patients with abnormal values or clinically relevant abnormal values

Vital signs, physical examinations, or other safety-relevant data observed at screening, baseline, during the course of the trial and at the end-of-trial evaluation will be assessed with regard to possible changes compared to findings before start of treatment.

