5.2.6.2 Adverse event collection and reporting

AE Collection

The investigator shall maintain and keep detailed records of all AEs in the patient files. The following must be collected and documented on the appropriate CRF(s) by the investigator:

- From the time of first dose of trial drug administration in the extension trial until the individual patient's end of trial:
all AEs (serious and non-serious) and all AESIs.
- After the individual patient's end of trial:
the investigator does not need to actively monitor the patient for new AEs but should only report any occurrence of cancer and trial treatment related SAEs and trial treatment related AESIs of which the investigator may become aware of by any means of communication, e.g. phone call. Those AEs should be reported on the BI SAE form (see [Figure 5.2.6.2:1](#)), but not on the CRF.

[figure not shown]

Figure 5.2.6.2: 1 Adverse event collection and reporting

However, patients who discontinue trial medication prematurely and agree to be contacted further should be followed up as described in [section 3.3.4.1](#), withdrawal from trial treatment. From then on until the initially planned completion date of each individual patient the investigator must report all deaths/fatal AEs regardless of relationship, related SAEs and related AESIs the investigator becomes aware of.

AE reporting to sponsor and timelines

The investigator must report SAEs, AESIs, and non-serious AEs which are relevant for the reported SAE or AESI, on the BI SAE form immediately (within 24 hours) to the sponsor's unique entry point (country specific reporting process will be provided in the ISF). The same timeline applies if follow-up information becomes available. In specific occasions the investigator could inform the sponsor upfront via telephone. This does not replace the requirement to complete and send the BI SAE form.

With receipt of any further information to these events, a follow-up SAE form has to be provided. For follow-up information the same rules and timeline apply as for initial information.

Information required

For each AE, the investigator should provide the information requested on the appropriate eCRF pages and the BI SAE form, if applicable.

The following should also be recorded as an (S)AE in the CRF and BI SAE form (if applicable):

- Worsening of the underlying disease or of other pre-existing conditions

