#### **4. CHANGES IN THE PLANNED ANALYSIS OF THE STUDY**

The population label for Treated Set (TS) is updated to be Safety Analysis set (SAF) based on current project definition. Thus the TS-RT for re-induction treatment becomes SAF-RT, and TS-MT for maintenance treatments becomes SAF-MT.

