### **Overall Maintenance Treatment Period**

The overall maintenance treatment period applies to all patients taking at least one dose of maintenance treatment regardless of flare occurrence. This period will be considered to understand long-term efficacy and safety of spesolimab.

Table 6.1: 4 Flow chart of analysis phases for overall maintenance treatment period

Study analysis phase	Description	Start (included)	End (included)
Screening  phase	Screening	Earliest of (Date of informed consent, first screening procedure)	Date/time of injection of first maintenance study drug minus 1 minute
Maintenance treatment phase & Residual effects period	Maintenance on-treatment period	Date/time of injection of first maintenance study drug (Day 1 for maintenance)	Date of end of (infusion or injection) of last administered spesolimab + 112 days at 23:59
Follow-up  phase	Off-treatment period	Date of end of (infusion or injection) of last administered spesolimab + 113 days at 12:00 a.m.	Latest of: i) Date of End-of-Study visit; ii) last contact date on End of Study page at 23:59

Dates are defined individually per patient. If more than one date is associated with a specific visit, measurements associated with a specific date are assigned to a study analysis phase according to the rules specified in the table. An analysis phase will not extend beyond the start date of the following phase.

 The off-treatment period (i.e. Follow-up phase) only exists if the trial completion date is after the date of end of last injection or infusion + 112 days.

 The screening phase does not exist for re-induction treated patients who subsequently receive maintenance treatment.

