#### 7.8.1 Adverse events

AEs will be coded with the most recent version of MedDRA.

The analyses of AEs will be descriptive in nature. All analyses of AEs will be based on the number of patients with AEs and not on the number of AEs. System organ classes (if applicable) will be sorted according to the standard sort order specified by the EMA, preferred terms (if applicable) will be sorted by total frequency (within system organ class).

For further details on summarization of AE data, please refer to "Handling and summarization of adverse event data for clinical trial reports and integrated summaries" ([4](#)) [*KM Asset BI-KMED-BDS-HTG-0041*] and "Handling of missing and incomplete AE dates" ([3](#)) [*KM Asset BI-KMED-BDS-HTG-0035*].

The analysis of AEs will be based on the concept of treatment emergent AEs. This means that all AEs will be assigned to the screening phase, re-induction on-treatment period (i.e. re-induction treatment phase plus REP), maintenance on-treatment period (i.e. maintenance treatment phase plus REP) or off-treatment period (i.e. follow-up) as defined in [Section 6.1](#). Adverse events occurring in the maintenance and re-induction periods will be separately described. Since only the start date of an AE is collected (without start time), any AE occurrence on the same day as the first re-induction or first maintenance spesolimab administration will be assigned to the respective on-treatment period. For patients who switch directly to maintenance treatment at week 12 of the re-induction period, adverse events occurring on this first day of maintenance treatment will be included in summaries of the maintenance period only. Exposure-adjusted adverse event incidence rates (per the primary endpoint) will be calculated using the following approach:

- 1) The exposure adjusted incidence rate (per 100 subject years) of a selected treatment emergent adverse event is defined as the number of subjects experiencing the adverse event per treatment group during time at risk divided by the total time of subjects at risk in that treatment group to contribute the event to the analysis multiplied by 100 (per 100 subject years), where:
  - 2) Time at risk [subject years] = (date of onset of AE – study drug start date + 1) / 365.25

For safety analysis on the post-flare treatment periods: Time at risk [subject years] = (date of onset of AE – first i.v. disease flare treatment start date + 1) / 365.25

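### The protocol counts pre-dose AEs that worsen on treatment as treatment-emergent; the SAP has no worsening rule, so an AE recorded at screening may drop out of the primary rate or get zero or negative time at risk

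*Protocol*

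**What the plan says.** The primary endpoint is the exposure-adjusted rate of patients with a TEAE up to week 336 of maintenance. Protocol 7.3.1 refers its analysis to protocol 7.3.4, which holds two rules:

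- Onset rule: "All adverse events with an onset between start of treatment and end of the residual effect period (REP") belong to the on-treatment period.
- Worsening rule: "Adverse events that start before first drug intake and deteriorate under treatment will also be considered as" treatment-emergent.

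SAP 7.8.1 keeps only the first. It says of its treatment-emergent concept: "This means that all AEs will be assigned to the screening phase, re-induction on-treatment period", maintenance on-treatment period or off-treatment period. In SAP Table 6.1: 4 the screening phase ends at "Date/time of injection of first maintenance study drug minus 1 minute". Step 2 of the rate calculation reads "Time at risk [subject years] = (date of onset of AE" minus the study drug start date plus 1), divided by 365.25. Neither place mentions worsening.

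SAP 4 lists one change to the planned analysis: "The population label for Treated Set (TS) is updated to be Safety Analysis set (SAF"), with the matching renaming of its subsets.

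On data collection, protocol 5.2.6.2 starts AE recording "From the time of first dose of trial drug administration in the extension trial until" the patient's end of trial. The flow chart nevertheless ticks adverse events at V1 and V1a, and protocol 6.2.1 has patients asked at V1a about possible AEs since V1.

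**The concern.** The two documents define the event behind the primary endpoint differently, and the difference is not declared. Because the screening visits ask about AEs and the SAP has a screening phase to hold them, an AE record with a pre-dose onset can exist.

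Suppose such an AE worsens after dosing and stays as one record. Under the SAP it is not treatment-emergent. Under the protocol it is, but the SAP formula then starts the clock after the event. No rule in either document resolves this, so whoever programs the rate would have to choose. Worsening on drug is something a long-term safety table should show.

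**Working it through.** **1. The rules side by side, for one record with pre-dose onset that worsens on treatment**

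| | Protocol 7.3.4 | SAP 7.8.1 and 6.1 |
|---|---|---|
| Treatment-emergent? | Yes | No: screening phase |
| Date used for time at risk | Not stated | Onset date |
| Declared as a change? | n/a | Not in SAP 4 |

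For the maintenance period this concerns patients who enter maintenance directly. SAP Table 6.1: 4 gives re-induction patients no screening phase before maintenance.

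**2. Time at risk if the protocol rule is applied with the SAP formula**

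V1 is planned for Day -7 to -2 and V1a for Day -2 to -1 (Flow Chart 1A). For onset d days before first dose, time at risk = -d + 1 days:

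| Onset | Days | Years (days / 365.25) |
|---|---|---|
| 1 day before | 0 | 0 |
| 2 days before | -1 | -0.0027 |
| 7 days before | -6 | -0.0164 |

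The value is zero for the day before dosing and negative for anything earlier. Timing the event at its worsening removes the problem: worsening on Day 15 (assumed) gives 15 / 365.25 = 0.041 years.

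**3. Possible effect on the any-TEAE rate**

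The plan states no expected rate, so there is no figure to reproduce. The illustration takes N = 80 from the synopsis. Everything else is assumed: exponential first-TEAE hazard h of 0.5, 2 or 4 per year; follow-up T of 0.5, 1 or 6.44 years (2353 / 365.25); and k = 2 or 8 patients with onset 7 days before dosing and worsening on Day 15. Let p = 1 - exp(-hT). Rates are per 100 patient-years:

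- Event dropped: 100 × Np / (Np/h) = 100h
- Counted at original onset: 100 × [(N-k)p + k] / [(N-k)p/h - 6k/365.25]
- Timed at worsening: 100 × [(N-k)p + k] / [(N-k)p/h + k(1 - exp(-15h/365.25))/h]

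For h = 2, T = 1, k = 2: p = 0.865 and the numerator of the last two is 78 × 0.8647 + 2 = 69.44. The denominators are 33.72 - 0.03 = 33.69 and 33.72 + 0.08 = 33.80.

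| h, T, k | Dropped | Original onset | At worsening |
|---|---|---|---|
| 2, 1, 2 | 200.0 | 206.1 | 205.5 |
| 2, 1, 8 | 200.0 | 226.7 | 223.4 |
| 0.5, 0.5, 8 (largest effect) | 50.0 | 75.4 | 74.4 |
| 4, 6.44, 2 (smallest effect) | 400.0 | 410.9 | 408.7 |

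Over the whole grid, dropping the event instead of timing it at worsening lowers the rate by about 2% (1 - 400.0/408.7) to 33% (1 - 50.0/74.4). Using the original onset instead raises it by less than 3%. The share of patients expected to have another TEAE, p, runs from 22% to nearly 100%.

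**4. Single terms.** For a preferred term with 1 to 5 cases (assumed), one lost worsening is 1/1 to 1/5 of the count, or 100% to 20%.

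**5. Who is touched by the meaning of first drug intake.** Protocol Table 1.4:5 shows 1 + 2 + 4 + 2 = 9 responders to re-induction and 5 + 2 + 6 + 5 = 18 direct maintenance patients. If all 9 went on, 9/27, a third of these maintenance patients, had already taken drug in this trial before maintenance began.

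**The case against.** The strongest reply is that the data are already recorded in a way that avoids the conflict. Protocol 6.2.1 puts new findings at screening on the baseline-condition page. Protocol 5.2.6.2 treats abnormalities present before trial inclusion as baseline conditions and asks for worsening of pre-existing conditions to be recorded as an AE. If that is a new record, it has an on-treatment onset, enters the numerator and has positive time at risk. The SAP also assumes familiarity with the protocol and defers AE detail to sponsor guidance that the reader cannot see.

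Most of this stands for baseline conditions. It does not settle a symptom logged as an AE at V1 or V1a, and neither document says that worsening gets its own record and date. If it always did, the worsening sentence in 7.3.4 would not be needed.

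Four stronger readings are tempting but not supported:

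- **That the SAP formula gives large negative times.** Onset 84 days before maintenance would give -83 days, but an AE starting in re-induction begins after first drug intake in this trial, so the plain wording of the protocol rule does not reach it. Onset 10 days before Day 1 would give -9 days, but it lies outside the screening period of up to 7 days.
- **That such a re-induction AE disappears.** It is reported as a re-induction TEAE, and SAP 7.8.1 summarises AEs by maximum intensity.
- **That worsening liver enzymes would be missed.** SAP 7.8.2 tabulates worst RCTC grade against baseline and AST/ALT threshold counts from laboratory values. Under SAP 5 the maintenance safety baseline is the last value before maintenance.
- **That the SAP admits no worsening date exists.** The sentence "Since only the start date of an AE is collected (without start time), any AE occurrence on the same day" is about a missing clock time and does not bear on worsening.

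**Conclusion.** The inconsistency is real and concerns the definition behind the primary endpoint, but it is narrow. It affects an AE recorded before first dose, kept as one record with its original onset, that worsens on treatment. Such an event may be left out of the numerator or, if counted, gets 0 to about -6 days at risk. How many exist depends on CRF practice, which the documents do not settle.

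The effect on the any-TEAE rate is probably small, because a patient is lost from the numerator only if no other TEAE occurs. The 2% to 33% range rests on assumed hazards, follow-up and case counts, and its upper end is not a forecast. Individual terms with few cases are more sensitive. The analysis is descriptive, so no test is affected.

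A second, related gap remains: the plan does not say whether first drug intake means the first dose in the trial or in the period for re-induction patients entering maintenance. The correction is worth making because the two definitions conflict and the repair is cheap.

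**What to change.** 1. In SAP 7.8.1, state that an AE that starts before a period's first dose and whose RCTC grade increases in that period is treatment-emergent in it. Use the date of worsening for phase assignment and time at risk.
2. In protocol 5.2.6.2, state that worsening of an AE already recorded, at screening or in re-induction, is entered as a new AE with its own onset date.
3. Say which first drug intake applies to re-induction patients who enter maintenance.
4. If the worsening rule is not wanted, list its removal in SAP 4 instead.

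The cost is a few sentences in the two documents and a small derivation change, plus a check of existing AE records with onset before first dose. SAP 7.8.1 counts patients and not events, so a second record for the same AE does not count a patient twice within a period.
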